Our study plans to treat all patients initially with a one month trial of migraine diet and then randomize treatment naive patients with vestibular migraine to an 8 week trial of an escalating dose of either nortriptyline or topiramate followed by an 8 week crossover to the other drug. Response to therapy will be quantified by the Migraine Specific Quality of Life (MSQ), (Renabsbaum, 2013) Dizziness Handicap Inventory (DHI) (Jacobson, 1990; Vereeck, 2006) and Motion Sensitivity Questionnaire (MoSQ) (Dannenbaum, 2011) administered at multiple time points during the study. Three groups of patients eligible for the study will include 1) patients with Neuhauser dVM; 2) patients with pVM; and 3) patients with dizziness that falls outside the Neuhauser criteria (non-Neuhauser vestibular migraine or nNVM) but is still felt by the investigators to be most likely due to a migraine variant.

Meniere's syndrome is a completely different entity from vestibular migraine. Meniere's involves episodic vertigo associated with a fluctuating hearing loss, ear fullness and tinnitus. In contrast, vestibular migraine, also known as migraine associated dizziness involves episodic dizziness and imbalance at times associated with headache, but without hearing change. Meniere's is a disorder of the inner ear, while vestibular migraine is a migraine that affects the part of the brain dealing with balance.

Please save frequently

b) Describe any animal experimentation and findings leading to the formulation of the study, if

Protocol Title: A Prospective randomized cross-over trial of nortriptyline and topiramate in the initial treatment of vestibular migraine

there is no supporting human data.

n/a

2. Purpose of the study

a) **Provide a brief lay summary of the project in <200 words. The lay summary should be readily understandable to the general public.**

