Due to known drug interactions, patients taking the following medications will be excluded. Nortriptyline: monoamine oxidase inhibitors (MAO) such as phenelzine. Patients on oral contraceptives will be asked to use a secondary method as nortriptyline can reduce the effectiveness of oral contraceptives.

Topiramate: acetazolamide (kidney stones), digoxin

An electronic health record (EPIC) will be used for secure collection of all patient data. Questionnaires filled out by patients will be scanned into EPIC.

A sample size of 100, which nets 90 subjects into the randomized medication trial (two equal groups of 45 subjects each), yields a power of 82% to detect a difference in patient-reported effectiveness/acceptability between the nortriptyline and topiramate groups after two months of medication use. This sample size estimate assumes 60% of subjects using nortriptyline report it as effective/acceptable, in contrast to half as many subjects (or 30%) using topiramate. The power calculation is based on a two-sized Z-test with pooled variance and targeted significance level (alpha) of 0.05. The expected difference in outcome between the two groups is based on our prior research ([name], 2012).

Adverse effects of the two drugs will be assessed. Specifically, the following known side effects will be asked about and recorded.

Nortriptyline: somnolence, weight gain, dry mouth, blurred vision

Topiramate: Weight loss, parasthesias, forgetfulness, nausea, diarrhea, fatigue

The subjects will be allowed to maintain therapy or taper off the drugs. It is anticipated that those that derive benefit from the drugs will choose to stay on them. All patients will have the option of remaining under our care outside of the study.

c) If the proposed study is a clinical trial where a drug, vaccine, device or other treatment is compared to a placebo group or comparison treatment group, what are the guidelines or endpoints by which early decisions regarding efficacy or lack of efficacy can be made? For example, it may be reasonable to stop enrollment on a study when efficacy has already been clearly demonstrated, to avoid unnecessary enrollments of additional subjects. Alternatively, it may be reasonable to stop enrollment when it is clear that efficacy will never be demonstrated, given the statistical power of the study as designed. Describe the guidelines that are in place to assist in making these determinations, if relevant to the proposed study.

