Men and women aged 18 to 70 with untreated vestibular migraine variant as diagnosed by history.

Identify exclusion criteria.

Patients with allergies to nortriptyline or topiramate and their analogs or medication interactions that preclude their use. Patients under the care of a psychiatrist. Patients who are pregnant or trying to become pregnant. Patients taking more than 5 prescription medications. Patients with cancer. Patient has a history of immunodeficiency. Patient has a history of substance abuse within the preceding 6 months prior to screening. Patient has used an investigational drug or device in the the 3 months prior to screening. Patient is using marijuana for medical or other uses. Patient has any other clinically significant illness or medical condition that, in the investigator's opinion, would prohibit the subject from participating in the study. Patient with traumatic brain injury.

Due to known drug interactions, patients taking the following medications will be excluded. Nortriptyline: monoamine oxidase inhibitors (MAO) such as phenelzine. Patients on oral contraceptives will be asked to use a secondary method as nortriptyline can reduce the effectiveness of oral contraceptives.

Topiramate: acetazolamide (kidney stones), digoxin

Exclude subjects with liver dysfunction, kidney dysfunction and glaucoma (per the risks associated with topiramate).

i) Compensation. Explain the amount and schedule of compensation, if any, that will be paid for participation in the study. Include provisions for prorating payment.

Protocol Title: A Prospective randomized cross-over trial of nortriptyline and topiramate in the initial treatment of vestibular migraine

\$60 will be paid to each patient per visit that they participate in the research study. Checks will be sent monthly after each visit. Costs of the medication is standard of care. The subject will be responsible for picking up and paying for the medication at their preferred pharmacy.

j) Describe who will cover study related costs. Explain any costs that will be charged to the subject.

Association for Migraine Disorders has funded the study and will cover all costs.

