Allergic - Skin rash, petechiae, urticaria, itching, photosensitization (avoid excessive exposure to sunlight); edema (general or of face and tongue), drug fever, cross-sensitivity with other tricyclic drugs.

Hematologic - Bone marrow depression, including agranulocytosis; eosinophilia; purpura; thrombocytopenia.

Gastrointestinal - Nausea and vomiting, anorexia, epigastric distress, diarrhea, peculiar taste, stomatitis, abdominal cramps, black-tongue.

Endocrine - Gynecomastia in the male, breast enlargement and galactorrhea in the female; increased or decreased libido, impotence; testicular swelling; elevation or depression of blood sugar levels; syndrome of inappropriate ADH (antidiuretic hormone) secretion.

Other - Jaundice (simulating obstructive), altered liver function; weight gain or loss; perspiration; Suicide

Serotonin Syndrome (>>>>)

Topiramate: Possible adverse reactions

oral contraceptive pills may have reduced efficacy when used with topiramate

paresthesia (35-50%) and taste perversion (10-15%)

Acute Myopia and Secondary Angle Closure Glaucoma, Visual Field Defects, Oligohidrosis and Hyperthermia, Metabolic Acidosis, Suicidal Behavior and Ideation, Cognitive/Neuropsychiatric Adverse Reactions (including cognitive dysfunction, psychiatric/behavioral disturbances and somnolence/fatigue), Hyperammonemia and Encephalopathy, Kidney Stones. Additionally, the adverse effects section in the package insert Table 10 (incidence of 2-5%) includes fatigue, hypoesthesia, language problems, nausea, diarrhea, decreased weight, arthralgia anorexia, somnolence, difficulty with memory, difficulty with concentration/attention.

Patients will be asked to wean off of drug over the course of one week if they have been on the drug more than a week. Specific issues we will watch for include:

Nortriptyline: At the low dosages used in this study, abrupt withdrawal has not been shown to be harmful.

Topiramate: Acute myopia due to secondary angle closure glaucoma has been rarely reported in acute withdrawal.

4. Use of FDA approved devices. Please include the clinical adverse events (AEs) associated with each of the devices with an indication of frequency, severity and reversibility. This information can often be found in the Investigator(s) brochure. NOTE: Include any likely adverse effects associated with procedures that subjects may experience while in the study.

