If patients are pregnant, or become pregnant, they cannot take part in this research study. It is important that they let the research study doctor know if they are breast-feeding. If patients are pregnant or think they are pregnant, it is important for them to let the investigator know immediately.

If patients are sexually active during their participation in the research, they will use effective measures (chosen in consultation with their health care provider) to avoid becoming pregnant.

TOPAMAX (topiramate) can cause fetal harm when administered to a pregnant woman. Data from pregnancy registries indicate that infants exposed to topiramate in utero have an increased risk for cleft lip and/or cleft palate (oral clefts).

Nortriptyline is category D (from Pregnancy and Lactation text book - there is not a manufacturer designation). Information from the PI states "Safe use of nortriptyline hydrochloride during pregnancy and lactation has not been established; therefore, when the drug is administered to pregnant patients, nursing mothers, or women of childbearing potential, the potential benefits must be weighed against the possible hazards. Animal reproduction studies have yielded inconclusive results. Information from the above cited text states possible cardiovascular anomalies.

11. Data Safety Monitoring

Federal regulations require that when appropriate, the research protocol makes adequate provisions for monitoring the data to ensure the safety of participants. Monitoring should be commensurate with risks and with the size and complexity of the research, and could range from no plan needed to an independent data safety monitoring board. Please refer to [SLU Guidelines for Data and Safety Monitoring](#) as you complete the questions below.

a. Is there a Data Monitoring Committee (DMC) or Board (DSMB)? N

If yes, please provide the following information (labeled a-g): a) the composition of the board (degrees/qualifications of members), b) whether the board is independent from the sponsor and research team or not, c) frequency of meetings and issuance of reports to sites, d) assurance that the board is reviewing aggregate safety data and making recommendations regarding study continuance, e) provisions for ad hoc meetings if needed, f) who is reviewing SAEs in real time (MD or DO), and g) stopping/halting rules (if any exist).

A DSM charter can be referenced for all items except for "f) who is reviewing SAEs in real time."

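### Sections 3b and 8h attribute the oral contraceptive interaction to nortriptyline and section 9.3 attributes it to topiramate, leaving unclear which patients and treatment periods the back-up contraception request covers

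*Combined protocol and SAP*

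**What the plan says.** Sections 3b (Study Procedures) and 8h (Inclusion and Exclusion Criteria) carry the same short block on drug interactions, sorted by drug. Under the nortriptyline label it names monoamine oxidase inhibitors and then adds: "Patients on oral contraceptives will be asked to use a secondary method as nortriptyline can reduce the effectiveness of oral contraceptives". The line for the other drug reads, in full, "Topiramate: acetazolamide (kidney stones), digoxin".

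Section 9.3 (Risks, FDA approved drugs) lists possible adverse reactions for each drug. The topiramate list begins with the statement that "oral contraceptive pills may have reduced efficacy when used with topiramate". The nortriptyline list, which is longer and arranged by body system, says nothing about contraceptives.

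Section 9.10 (Reproductive Risks) says "TOPAMAX (topiramate) can cause fetal harm when administered to a pregnant woman" and cites pregnancy-registry data on oral clefts. It gives nortriptyline as pregnancy category D. It also has a general instruction that is not tied to either drug: "If patients are sexually active during their participation in the research, they will use effective measures", to be chosen with the patient's health care provider. That instruction mentions neither a second method nor the interaction.

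**The concern.** The request for a second contraceptive method is the only action in the protocol that addresses this interaction. Its label and its stated reason both point to nortriptyline, while the protocol's own risk section points to topiramate. A coordinator who works from the interaction block and one who works from the risk section would give a patient different explanations. They might also differ on whether a patient assigned to topiramate needs to be asked.

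The matter bears on safety because the protocol states a fetal risk for topiramate and does not treat nortriptyline as established to be safe in pregnancy. The attribution therefore matters whichever drug is involved. It also matters because patients change drugs. Section 1a describes an "8 week trial of an escalating dose of either nortriptyline or topiramate followed by an 8 week crossover to the other drug", and section 3b lets a patient who cannot tolerate the first drug move at once to the other, arranged through the pharmacy by telephone with no clinic visit. The protocol does not say whether contraceptive advice is repeated or revised at that point.

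**Working it through.** No arithmetic applies. The check sets the passages side by side and then asks who would be asked under each reasonable reading.

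**Step 1. Attribution by section**

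| Section | Nortriptyline and oral contraceptives | Topiramate and oral contraceptives |
|---|---|---|
| 3b, Study Procedures | Stated: "nortriptyline can reduce the effectiveness of oral contraceptives" | Not mentioned |
| 8h, Eligibility | Stated, same sentence | Not mentioned |
| 9.3, Risks | Not mentioned | Stated: "oral contraceptive pills may have reduced efficacy when used with topiramate" |
| 9.10, Reproductive Risks | Interaction not mentioned | Interaction not mentioned |

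Each section that mentions the interaction names one drug, and the sections do not name the same drug. Because the nortriptyline sentence appears in two places, correcting only one of them would leave the inconsistency.

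**Step 2. Are the statements logically exclusive?** They are not. An interaction with one drug does not rule out one with the other. If both statements are true, each section is incomplete. If only one is true, at least one section is wrong. In either case the text needs reconciling, and the protocol alone does not show which case applies.

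**Step 3. Who is asked under each reading of the request**

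| Patient on an oral contraceptive | Broad reading (all users, asked at eligibility) | Narrow reading (only when on nortriptyline) |
|---|---|---|
| Starts nortriptyline | Asked | Asked |
| Starts topiramate | Asked | Not asked at the start |
| Moves from nortriptyline to topiramate | Already asked | Already asked; whether the request continues is not stated |
| Moves from topiramate to nortriptyline | Already asked | Asked only if raised at the switch |

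On the broad reading nobody is missed, but the reason given still does not match section 9.3. On the narrow reading the main gap is the patient who starts topiramate. A smaller uncertainty is how long the request lasts after a move away from nortriptyline.

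**Step 4. Size.** Section 3b plans 45 patients per group, so about 45 would start topiramate. That is not a count of patients affected. It includes men and patients up to age 70. The number affected would be 45 multiplied by the share using oral contraceptives and by the share whose staff apply the narrow reading. The documents give neither share, so no number can be computed. Actual harm would need further steps: no second method used, loss of contraceptive efficacy, and conception.

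**The case against.** The strongest reply is that a reason is not a scope. The grammatical subject of the sentence is patients on oral contraceptives, with no condition on assignment; the mention of nortriptyline only explains why they are asked. The sentence also sits in eligibility text that applies to every patient. Section 3b puts randomization at the one-month point for most patients, so the assigned drug is usually unknown when eligibility is judged. Read this way, the request reaches every contraceptive user and carries through any later switch. Section 9.10 adds a general contraception instruction for all sexually active patients, and section 8h excludes those who are pregnant or trying to become so.

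Most of this stands. A reader might infer that patients on topiramate, half of those randomized, are left without the request. The documents do not support that. The literal sentence includes those patients, section 9.10 applies to them, and 45 of 90 is an arm size rather than an exposed group. A reader might also infer that a phone switch necessarily makes the earlier advice wrong. That follows only if the advice was specific to the first drug, which is the point left unclear. Nor can it be said that patients are given the wrong reason: the consent form and the follow-up phone script listed in the protocol were not available for this review and may be correct.

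Two things remain. The stated reason conflicts with section 9.3 on any reading. And a safety instruction should not rely on staff disregarding both the drug label above it and the reason within it. The general instruction in section 9.10 does not close the gap, since a patient could reasonably regard the pill alone as an effective measure.

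**Conclusion.** The protocol is wrong as written on this point and should be corrected. Sections 3b and 8h attribute the oral contraceptive interaction to nortriptyline, section 9.3 attributes it to topiramate, and none names both. That much is certain from the text.

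The consequence is less certain. A missed request for a second method is possible, mainly for a patient who starts topiramate under staff who read the sentence as specific to nortriptyline. It depends on that narrow reading being applied in practice and on the consent form and phone script not already settling the matter; neither can be verified from the protocol. The number of patients concerned cannot be computed. The point does not touch the power calculation or the analysis. It ranks as something that should be fixed rather than a fault that invalidates the plan, and no position is taken on which attribution is correct.

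**What to change.** - Check sections 3b, 8h and 9.3 against the two package inserts already attached in section 16, and revise them so that all three name the same drug or drugs for this interaction.
- State explicitly which patients the request for a second method covers and in which treatment periods, including after a switch arranged by phone under section 3b.
- Check that the consent form and the follow-up phone script agree with the reconciled text, and amend them only if they do not.

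The choice of attribution and of any clinical rule belongs to the investigator, working from the inserts. The cost is a wording amendment to the protocol, plus the consent form or script if the check finds a mismatch. It adds no visits, procedures or data collection.

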*** Risks ***

9. Risks

There is no research that can be considered totally risk free (e.g., a potential risk of breach of confidentiality). Therefore, when describing the risk, the lowest level of risk is "no more than minimal risk".

Page numbers from a sponsor's protocol/grant may be referenced in 9.1, 9.2, 9.3, and 9.4.

1. Use of investigational devices. Please include the clinical adverse events (AEs) associated with each of the devices with an indication of frequency, severity and reversibility. This information can often be found in the Investigator(s) brochure. NOTE: Include any likely adverse effects associated with procedures that subjects may experience while in the study.
2. Use of investigational drugs. Please include the clinical AEs associated with each of the drugs with an indication of frequency, severity and reversibility. This information can often be found in the Investigator(s) brochure. NOTE: Include any likely adverse effects associated with placebos or washout periods that subjects may experience while in the study.
3. Use of FDA approved drugs, reagents, chemicals, or biologic products. Please include the clinical AEs associated with each of the drugs with an indication of frequency, severity and reversibility. This information can often be found in the package insert provided by the manufacturer. NOTE: Include any likely adverse effects associated with placebos or washout periods that subjects may experience while in the study.

Nortriptyline: Possible adverse reactions

Cardiovascular - Hypotension, hypertension, tachycardia, palpitation, myocardial infarction,

Protocol Title: A Prospective randomized cross-over trial of nortriptyline and topiramate in the initial treatment of vestibular migraine

arrhythmias,
heart block, stroke.

Psychiatric - Confusional states (especially in the elderly) with hallucinations, disorientation, delusions; anxiety, restlessness, agitation; insomnia, panic, nightmares; hypomania; exacerbation of psychosis.

Neurologic - Numbness, tingling, paresthesias of extremities; incoordination, ataxia, tremors; peripheral neuropathy; extrapyramidal symptoms; seizures, alteration in EEG patterns; tinnitus.

Anticholinergic - Dry mouth and, rarely, associated sublingual adenitis; blurred vision, disturbance of accommodation, mydriasis; constipation, paralytic ileus; urinary retention, delayed micturition, dilation of the urinary tract.

Allergic - Skin rash, petechiae, urticaria, itching, photosensitization (avoid excessive exposure to sunlight); edema (general or of face and tongue), drug fever, cross-sensitivity with other tricyclic drugs.

Hematologic - Bone marrow depression, including agranulocytosis; eosinophilia; purpura; thrombocytopenia.

Gastrointestinal - Nausea and vomiting, anorexia, epigastric distress, diarrhea, peculiar taste, stomatitis, abdominal cramps, black-tongue.

Endocrine - Gynecomastia in the male, breast enlargement and galactorrhea in the female; increased or decreased libido, impotence; testicular swelling; elevation or depression of blood sugar levels; syndrome of inappropriate ADH (antidiuretic hormone) secretion.

Other - Jaundice (simulating obstructive), altered liver function; weight gain or loss; perspiration; Suicide

Serotonin Syndrome (>>>>)

Topiramate: Possible adverse reactions

oral contraceptive pills may have reduced efficacy when used with topiramate

paresthesia (35-50%) and taste perversion (10-15%)

Acute Myopia and Secondary Angle Closure Glaucoma, Visual Field Defects, Oligohidrosis and Hyperthermia, Metabolic Acidosis, Suicidal Behavior and Ideation, Cognitive/Neuropsychiatric Adverse Reactions (including cognitive dysfunction, psychiatric/behavioral disturbances and somnolence/fatigue), Hyperammonemia and Encephalopathy, Kidney Stones. Additionally, the adverse effects section in the package insert Table 10 (incidence of 2-5%) includes fatigue, hypoesthesia, language problems, nausea, diarrhea, decreased weight, arthralgia anorexia, somnolence, difficulty with memory, difficulty with concentration/attention.

Patients will be asked to wean off of drug over the course of one week if they have been on the drug more than a week. Specific issues we will watch for include:

Nortriptyline: At the low dosages used in this study, abrupt withdrawal has not been shown to be harmful.

Topiramate: Acute myopia due to secondary angle closure glaucoma has been rarely reported in acute withdrawal.

4. Use of FDA approved devices. Please include the clinical adverse events (AEs) associated with each of the devices with an indication of frequency, severity and reversibility. This information can often be found in the Investigator(s) brochure. NOTE: Include any likely adverse effects associated with procedures that subjects may experience while in the study.

5. Describe any risks related to performing study procedures. Please include all investigational, non-

Protocol Title: A Prospective randomized cross-over trial of nortriptyline and topiramate in the initial treatment of vestibular migraine

investigational, and non-invasive procedures (e.g., surgery, blood draws, treadmill tests).

n/a

6. Describe any risks related to the use of radioisotopes/radiation-producing machines (e.g., X-rays, CT scans, fluoroscopy).

7. Describe why this investigational compound/drug/device/procedure's risks/benefits are potentially better than standard of care or other common alternatives. Any standard treatment that is being withheld must be disclosed and the information must be included in the consent form. *?HELP?*

This drug is standard of care so the risks/benefits are identical to that of standard of care.

8. Describe any psychological, social, or legal risks the subject may experience. *?HELP?*

Risk of Questionnaires:

Some questions on the questionnaires may make patients feel uncomfortable, they may not answer any question they do not feel comfortable answering

Loss of Confidentiality

Page numbers from a sponsor's protocol/grant may be referenced in 9.9 and 9.10.

9. Special Precautions. Describe the planned procedures for protecting against or minimizing potential risks. If appropriate, include the standards for termination of the participation of the individual subject. Discuss plans for ensuring necessary medical or professional intervention in the event of adverse effects to the subjects.

Patients will be closely followed while they are on study and can stop or change medications if they do not like the medications effects that they are on. You will be given the Columbia Suicide Severity Rating Scale at each appointment to evaluate any changes in mood and behavior related to suicidal thoughts. [name] will be available to evaluate and treat or refer to a specialist for any adverse reactions.

10. Reproductive Risks.

a. Please list the pregnancy category of any drugs or N/A.

D

Protocol Title: A Prospective randomized cross-over trial of nortriptyline and topiramate in the initial treatment of vestibular migraine

b. Please describe any reproductive risk associated with any part of the research study. Include any data from other studies (animal or human).

If patients are pregnant, or become pregnant, they cannot take part in this research study. It is important that they let the research study doctor know if they are breast-feeding. If patients are pregnant or think they are pregnant, it is important for them to let the investigator know immediately.

If patients are sexually active during their participation in the research, they will use effective measures (chosen in consultation with their health care provider) to avoid becoming pregnant.

TOPAMAX (topiramate) can cause fetal harm when administered to a pregnant woman. Data from pregnancy registries indicate that infants exposed to topiramate in utero have an increased risk for cleft lip and/or cleft palate (oral clefts).

Nortriptyline is category D (from Pregnancy and Lactation text book - there is not a manufacturer designation). Information from the PI states "Safe use of nortriptyline hydrochloride during pregnancy and lactation has not been established; therefore, when the drug is administered to pregnant patients, nursing mothers, or women of childbearing potential, the potential benefits must be weighed against the possible hazards. Animal reproduction studies have yielded inconclusive results. Information from the above cited text states possible cardiovascular anomalies.

11. Data Safety Monitoring

Federal regulations require that when appropriate, the research protocol makes adequate provisions for monitoring the data to ensure the safety of participants. Monitoring should be commensurate with risks and with the size and complexity of the research, and could range from no plan needed to an independent data safety monitoring board. Please refer to [SLU Guidelines for Data and Safety Monitoring](#) as you complete the questions below.

a. Is there a Data Monitoring Committee (DMC) or Board (DSMB)? N

If yes, please provide the following information (labeled a-g): a) the composition of the board (degrees/qualifications of members), b) whether the board is independent from the sponsor and research team or not, c) frequency of meetings and issuance of reports to sites, d) assurance that the board is reviewing aggregate safety data and making recommendations regarding study continuance, e) provisions for ad hoc meetings if needed, f) who is reviewing SAEs in real time (MD or DO), and g) stopping/halting rules (if any exist).

A DSM charter can be referenced for all items except for "f) who is reviewing SAEs in real time."

If no, please justify why not.

Treatment is standard of care

b. Is there a Data Safety Monitoring Plan (DSMP)? N

Protocol Title: A Prospective randomized cross-over trial of nortriptyline and topiramate in the initial treatment of vestibular migraine

Note, if all relevant plan information is included in DSMB question above, select 'Yes' and state "see above" in the answer box.

If yes, provide details (labeled a-e) including: a) what types of data or events are captured and how are they documented, b) who is monitoring data, their independence/affiliation with the research and their degrees/qualifications, c) frequency of aggregate data review, d) who is reviewing SAEs in real time (MD or DO), and e) stopping/halting rules (if any exist).

If no, please justify why not.

Treatment is standard of care.

12. In case of international research (research outside of the U.S. or research on international populations (non-U.S.)), describe qualifications/preparations that enable you to evaluate cultural appropriateness and estimate/minimize risks to subjects. Include whether research is sensitive given cultural norms.

a. State any local laws/regulations governing Human Subjects Research in the country(ies) you will conduct the research and attach any relevant approvals. If none, state N/A.

b. Will there be language barriers and if so, how will they be addressed?

Note: If materials are to be distributed to subjects in their native language, please follow SLU's Guidance For Studies Involving Non-English Speaking Subjects.

NOTE: Export control laws include the transfer of technical information and data, as well as information and technology to foreign nationals. If this study has international components, contact the SLU Export Control Officer for direction on whether export control policies apply.

* * * Benefits/Alternatives, Procedures to Maintain Confidentiality and Privacy * * *

10. Benefits/Alternatives

a) Benefits. Describe the potential benefit(s) to be gained by the subjects and how the results of the study may benefit future subjects and/or society in general. Indicate if there is no direct benefit to the participants.

Patients may or may not benefit from this study. Future patients with vestibular migraines may benefit from the knowledge obtained from this study.

Protocol Title: A Prospective randomized cross-over trial of nortriptyline and topiramate in the initial treatment of vestibular migraine

b) Alternatives. Describe any alternative treatments and procedures available to the subjects should they choose not to participate in the study. If no such alternatives exist, please state that the alternative is nonparticipation. For some studies, such as record reviews, a description of alternatives would not be applicable.

The alternative is not participating.

both topiramate and nortriptyline are available and readily prescribed outside of this protocol.

11. Procedures to Maintain Confidentiality and Privacy

Federal regulations require that research materials be kept for a minimum of three (3) years and HIPAA documents be kept for a minimum of six (6) years after the closure of the study. For FDA-regulated or sponsored projects, the PI may be required to keep the data and documents for a longer time period.

Confidentiality

To determine whether adequate provisions for confidentiality of data are in place, the IRB must ensure that research materials are stored in appropriate locations throughout the study (during collection, transport/transmission, analysis and long term storage). Research information must be protected using appropriate safeguards based on identifiability of the data and risk associated with the study (See SLU IRB Confidentiality Guidelines).

For the questions below, please use the following definitions:

Anonymous/De-identified: data contain no identifiers, including code numbers that investigators can link to individual identities;

Coded: data in which (1) identifying information, such as name or social security number, has been replaced with a number, letter, symbol, or combination thereof (i.e., the code), and (2) a key to decipher the code exists enabling linkage of data to identifying information (e.g., a master list), and (3) the key (master list) is kept separately from coded data; AND/OR

Identifiable: data that includes personal identifiers (e.g., name, social security number), such that information could be readily connected to respective individuals.

a) Electronic (Computer) Data

Click "Add" to enter data security information for each type of electronic data that will be created in the study: anonymous/de-identified, coded, and/or identifiable (see definitions above).

To properly address this question, there should only be one listing of each type of data in the table. Depending on your project, you could have up to three types of data. See the SLU ITS Sensitive Data Guide for acceptable data security methods.

Not Applicable, No Electronic (Computer) Data

Protocol Title: A Prospective randomized cross-over trial of nortriptyline and topiramate in the initial treatment of vestibular migraine

Study IRB-approved Prior to New Question (Question N/A- Grandfathered)

b) Hardcopy (Paper) Data

Click "Add" to enter information for each type of hardcopy (paper) data that will be created in the study: anonymous/de-identified, coded, and/or identifiable (see definitions above).

To properly address this question, there should only be one listing of each type of data in the table. Depending on your project, you could have up to three types of data.

Not Applicable, No Hardcopy (Paper) Data

Study IRB-approved Prior to New Question (Question N/A- Grandfathered)

c) If a master list is used in this study (linking study codes to subject identifiers), explain: a) how and where you will secure the master list, b) how long it will be kept/when it will be destroyed, and c) provide a sample of the code.

All data will be coded data stored for research purposes will be coded with a master list kept separately on a secure network, all hard copy data will be kept in a locked file cabinet in a locked office and coded, with a master list kept separately.

The coded master list will be destroyed as soon as data collection is complete.

d) If data or specimens are being shared outside of the research team, indicate who will receive the material, specifically what they will receive (data or specimens), and if an agreement has been signed to cover the transfer. Note: unless covered under a Clinical Trial or other agreement, the transfer of data or specimens to an external entity will require an agreement. For the transfer of materials (specimens), a Materials Transfer Agreement (MTA) is used; for the transfer of data, a Data Use or Data Transfer Agreement is used. Please contact the Research Innovation Group at [contact] for assistance.

Association of Migraine Disorders is a recipient of data, but this organization will only have access to aggregate data.

e) If samples or data will be provided to SLU from an outside source, indicate whether you will have access to identifiers, and if so, how identifiable information is protected. Note: unless covered under another agreement (e.g., Clinical Trial Agreement or subcontract), the transfer of data or specimens from an external entity to SLU may require an agreement. For the transfer of materials (specimens), a Materials Transfer Agreement (MTA) may be required; for the transfer of data, a Data Use or Data Transfer Agreement may be required. Please contact the Research Innovation Group at [contact] for assistance.

n/a

f) If data will be collected via e-mail or the Internet, how will anonymity or confidentiality be affected? Describe how data will be recorded (i.e., will internet protocol (IP) addresses and/or e-mail addresses be removed from data?).

Protocol Title: A Prospective randomized cross-over trial of nortriptyline and topiramate in the initial treatment of vestibular migraine

g) If you will be audio/video recording or photographing subjects, provide a rationale as voiceprints and images of faces/unique body markings are considered identifiers. Describe confidentiality procedures, including any restricted access to images and/or the final disposition of the recordings/photos (destruction, archiving, etc.).

h) Describe any study-specific (non standard of care) information or documentation that will be put in the participants' medical records for this research (e.g., study visit notes, lab results, etc.). If none, state "not applicable". NOTE: documentation of research in Epic should be done in accordance with the SLUCare Epic Research Charting Policy and Clinical Workflow: Documenting Research Encounters in Epic.

not applicable

i) Are there any information security requirements identified in the project's RFP/Award Notice/Contract? This could include data security, technical safeguards, security controls, NIST, FISMA, CFR, etc. N

If yes, SLU ITS approval is required. Contact [contact] to start the approval process.

Privacy

Privacy refers to persons having control over the sharing of oneself with others.

j) Please indicate how participant privacy will be protected in this study (select all that apply):

Discussion of health related and/or personal information in a private room/area
 Research interactions/interventions are conducted in a private room/area

Use of drapes or other privacy measures

